Assessment or Procedure	Screening Period	Mainter	nance C	Sycle 1 ^b		Maintenance Subsequent Cycles Every 21 Days (±3)	≤30 Days after Last Dose of Study Treatment	Every 3 Months After Disease Progression
Day (Window)	-28 to -1	1	2°	8 (+1) ^c	15 (+2) °	1		
HIV. HBV. HCV. EBV serology P	X		-	(=.)	10 (±±)			
Urinalvsis ^q	X			As	clinically inc	dicated		
Maintenance treatment administration: Venetoclax + atezolizumab		۲r				X٢		
Prophylactic cranial irradiation		Xs				Xs		
Tumor response assessment	x ^t	х ^и				х ^и		×۷
PK/ADA		x See Appendix 3: Table 1				x See Appendix 3: Table 1	x See Appendix 3: Table 1	
Blood sample for biomarker analysis		x C1D1				C2D1, C3D1, C4D1, and every odd cycle	x See Appendix 4	
Tissue sample for biomarkers	X							
Optional tumor biopsy after induction treatment (if patient signs consent)		Any ti	me durii	ng mainte	enance trea	tment		
Optional tumor biopsy at the time of radiographic progression (if patient signs consent) ^w		At the	e time of	radiogra	phic progre	ession		
Optional tumor biopsy at other timepoints (RBR only)		Any time during treatment or survival follow-up						
Optional biopsy for DNA extraction (RBR only)						x		
Adverse events	x	X	X	X	Х	X	x×	x x
Concomitant medications	ХУ	ХУ	ХУ	Хy	ХУ	х ^у	х ^у	
Survival and anti-cancer therapy follow-up								XZ

ADA=anti-drug antibody; C=Cycle; CT=computed tomography; D=Day; ECOG=Eastern Cooperative Oncology Group; eCRF=electronic Case Report Form; EBV=Epstein-Barr virus; FFPE=formalin-fixed paraffin-embedded; HBcAb=hepatitis B core antibody; HBsAg=hepatitis B surface antigen; HBV=hepatitis B virus; HCV=hepatitis C virus; MRI=magnetic resonance imaging; PCI=prophylactic cranial irradiation; PCR=polymerase chain reaction; PD=pharmacodynamic; PD-L1=programmed death-ligand 1; PK=pharmacokinetic; PCI=prophylactic cranial irradiation; RBR=Roche Biosample Repository; RECIST=Response Evaluation Criteria in Solid Tumors; SCLC=small cell lung cancer; TLS=tumor lysis syndrome; TSH=thyroid-stimulating hormone.

- ^a Assessments should be performed before study drug infusion unless otherwise noted.
- ^b Cycle 1 must be performed within 5 days after the patient is enrolled. Screening assessments performed ≤ 96 hours before Cycle 1, Day 1 are not required to be repeated for Cycle 1, Day 1. In addition, ECOG performance status, limited physical examination, and local laboratory tests may be performed ≤ 96 hours before Day 1 of each cycle.
- Day 2, Day 8, and Day 15 assessments are not necessary during the dose-expansion phase, with the exception of PK sampling (refer to Appendix 4).
- ^d A pre-treatment tumor tissue (archival or freshly obtained) sample should be submitted before or within 4 weeks after enrollment. This specimen must be accompanied by the associated pathology report. Although any available tumor tissue sample can be submitted, it is strongly encouraged that representative tumor specimens in paraffin blocks (preferred) or 15 (or more) serial, freshly cut, unstained slides be submitted.
- Vital signs include pulse rate, respiratory rate, systolic and diastolic blood pressure, and temperature. Vital signs should be recorded as described in Section 4.5.4.
- ^f Includes evaluation of the head, eyes, ears, nose, and throat, and the cardiovascular, dermatologic, musculoskeletal, respiratory, gastrointestinal, genitourinary, and neurologic systems.
- ⁹ ECG recordings will be obtained when clinically indicated.
- ^h Hematology consists of CBC, including RBC count, hemoglobin, hematocrit, WBC count with differential (neutrophils, lymphocytes, eosinophils, monocytes, basophils, and other cells), and platelet count.
- At screening, the patient must have adequate hematologic and end-organ function defined by laboratory test results obtained within 14 days prior to enrollment.
- ^j Serum chemistry includes BUN or urea, sodium, potassium, magnesium, chloride, bicarbonate or total CO₂ if considered standard of care in the region, glucose, total bilirubin, ALT, AST, alkaline phosphatase, LDH, total protein, and albumin.
- ^k TLS assessment frequency during the dose-expansion phase will be determined based on a comprehensive review of data in the dose-escalation phase. TLS labs include serum creatinine, calcium, phosphorous, uric acid, potassium, and LDH. If the screening assessments were done within 3 days prior to Cycle 1 Day 1, there is no need to repeat the TLS panel at Cycle 1 Day 1. Refer to Appendix 9 and Appendix 11 for further instructions.
- ¹ Serum pregnancy test within 14 days before Cycle 1, Day 1.
- ^m Urine pregnancy tests; if a urine pregnancy test result is positive, it must be confirmed by a serum pregnancy test.
- ⁿ Total T3 will be tested only at sites where free T3 is not performed.

Venetoclax—F. Hoffmann-La Roche Ltd

Page 158 of 214 Protocol GO41864, Version 2

- P All patients will be tested for HIV prior to the inclusion into the study and HIV-positive patients will be excluded from the study. Patients with active hepatitis B (chronic or acute; defined as having a positive HBsAg test result at screening) will be excluded from the study. Patients with past or resolved HBV infection (defined as the presence of HBcAb and absence of HBsAg) are eligible; HBV DNA should be obtained in these patients prior to enrollment. Patients with HCV will be excluded from the study; patients who test positive for HCV antibody are eligible only if PCR is negative for HCV RNA.
- ^q Urinalysis by dipstick (specific gravity, pH, glucose, protein, ketones, and blood). Urinalysis is required at screening and will be obtained when clinically indicated.
- ^r For atezolizumab, the initial dose will be administered over 60 (±15) minutes. If the first infusion is well tolerated, subsequent infusions may be administered over 30 (±10) minutes (see Section 4.3.2.1). Venetoclax is administered QD for 21 days as described in Section 3.1.2; also see Section 4.3.2.2.
- ^s During the maintenance phase, PCI is permitted as per local standard of care and will be reported on the Prophylactic Cranial Irradiation eCRF.
- ^t CT scans (with oral/IV contrast unless contraindicated) or MRI scans of the chest and abdomen. A CT or MRI scan of the pelvis is required at screening and as clinically indicated or as per local standard of care at subsequent response evaluations. A CT (with contrast) or MRI scan of the head must be done at screening to evaluate CNS metastasis in all patients.
- ^u Perform every 6 weeks (± 7 days) for 48 weeks following Cycle 1, Day 1 and then every 9 weeks (± 7 days) thereafter, after completion of the Week 48 tumor assessment, regardless of treatment delays, until radiographic disease progression per RECIST v1.1, withdrawal of consent, death, or study termination by the Sponsor, whichever occurs first. Patients who continue treatment beyond radiographic disease progression per RECIST v1.1 will undergo tumor assessments *at the frequency described above* until study treatment is discontinued.
- If the patient discontinued study treatment for any reason other than radiographic disease progression per RECIST v1.1 (e.g., toxicity, symptomatic deterioration), tumor assessments will continue at the same frequency as would have been followed if the patient had remained on study treatment (i.e., every 6 weeks [± 7 days] for 48 weeks following Cycle 1, Day 1 and then every 9 weeks [± 7 days] thereafter) until radiographic disease progression per RECIST v1.1, withdrawal of consent, death, or study termination by the Sponsor, whichever occurs first, even if the patient starts another anti-cancer therapy after study treatment discontinuation, unless consent is withdrawn.
- Optional tumor biopsy at radiographic disease progression, if clinically feasible, preferably within 40 days of radiographic progression or prior to start of the next anti-cancer therapy, whichever occurs first.
- * All serious adverse events and adverse events of special interest, regardless of relationship to study drug, will be reported until 90 days after the last dose of study drug or initiation of new systemic anti-cancer therapy after the last dose of study drug, whichever occurs first. All other adverse events, regardless of relationship to study drug, will be reported until 30 days after the last dose of study drug or initiation of new systemic anti-cancer therapy after the last dose of study drug or initiation of new systemic anti-cancer therapy after the last dose of study drug or initiation of new systemic anti-cancer therapy after the last dose of study drug or initiation. In addition, the Sponsor should be notified if the investigator becomes aware of any serious adverse event or adverse event of special interest that is believed to be related to prior exposure to study treatment. These events should be reported through use of the Adverse Event eCRF.
- ^y From 7 days before screening until the treatment discontinuation visit. All such medications should be reported to the investigator and recorded on the Concomitant Medications eCRF.

Venetoclax—F. Hoffmann-La Roche Ltd Page 159 of 214 Protocol GO41864, Version 2

[•] Thyroid function testing (TSH, free T3, free T4) collected on Day 1 of Cycles 1, 4, 8, and 12, and every fourth cycle thereafter.

^z Survival follow-up information will be collected via telephone calls, patient medical records, and/or clinic visits every 3 months or more frequently until death, loss to follow-up, or study termination by the Sponsor, whichever occurs first. All patients will be periodically contacted for survival and new anti-cancer therapy information unless the patient requests to be withdrawn from follow-up (this request must be documented in the source documents and signed by the investigator). If the patient withdraws from the study, study staff may use a public information source (e.g., county records), when permissible, to obtain information about survival status only.

Appendix 2 Schedule of Activities: Dose-Escalation Induction + Maintenance (Arm B) and Dose-Expansion Induction + Maintenance

Assessment or	Screening	Treatment Period a						Treatment Discon.	Survival Follow- Up								
Procedure	Period		I	ndu Cyc	ction le 1			Ind Cy (±3	uction /cle 2 Days) ^b)		ır ±:	nduction Cycles 3–4 3 Days) ^b	Maint. Cycle 1	Maint. Subseq. Cycles Every 21 Days (±3)	≤30 Days after Last Dose of Study Treatment	Every 3 Months After Disease Prog.
					8 c	15 °			8 c	15 ^c							
Day (Window)	–28 to –1	1	2 ^c	3	(±1)	(±2)	1	2–3	(±1)	(±2)	1	2–3	15 ° (±2)	1	1		
Informed consent	X																
Pre-treatment tumor tissue specimen for further biomarker testing	X d																
Medical history and baseline conditions	x																
SCLC cancer history	x																
Vital signs ^e	X	Х	Х	X	X	Х	Х	X			Х	X		X	X	X	
Weight	X	Х					Х				Х			X	x	x	
Height	Х																
Complete physical examination ^f	x																
Limited physical examination		x			х	x	x				x			x	x	x	
ECOG performance status	x	x			x	x	x				x			x	x	x	

Atezolizumab—F. Hoffmann-La Roche Ltd

Page 161 of 214 Protocol GO41864, Version 2

Assessment or	Screening		Treatment Period ^a									Treatment Discon.	Survival Follow- Up				
Procedure	Period		I	ndu Cyc	ction :le 1			Ind Cy (±3	uction /cle 2 Days) ^b)		ار (±:	nduction Cycles 3–4 3 Days) ^b	Maint. Cycle 1	Maint. Subseq. Cycles Every 21 Days (±3)	≤30 Days after Last Dose of Study Treatment	Every 3 Months After Disease Prog.
Day (Window)	–28 to –1	1	2 ^c	3	8° (±1)	15° (±2)	1	2-3	8 ° (±1)	15° (±2)	1	2-3	15 ° (±2)	1	1		
12-lead ECG	x	X g	_		(/	/	-		(=-)	(/			10 (11)	xg		x ^g	
Hematology h	Xi	х	х		X	Х	х			x	Х		x	X	X	x	
Serum chemistry j	Xi	Х	х		X	х	х				Х			X	x		
TLS labs ^k	within 3 days of C1D1 or prior to C1D1 dose	x	x		x												
Coagulation test (aPTT or INR)	xi															x	
Pregnancy test (women of childbearing potential only)	xı	X m									x ^m			x ^m	x ^m	x ^m	
TSH, free T3, free T4 ⁿ	x	X o									хo			xo	х°	x	
HIV, HBV, HCV, EBV serology ^p	x																
Urinalysis q	Хd		-			-	-	-	-	Pe	rform	as clini	cally indicated		-		

Assessment or	Screening	Treatment Period a						Treatment Discon.	Survival Follow- Up									
Procedure	Period		I	ndu Cyc	ction le 1			Ind Cy (±3	uction /cle 2 Days) ^b)		וו (±	nduct Cycle 3–4 3 Day	ion es l s) ^b	Maint. Cycle 1	Maint. Subseq. Cycles Every 21 Days (±3)	≤30 Days after Last Dose of Study Treatment	Every 3 Months After Disease Prog.
Day (Window)	–28 to –1	1	2 ^c	3	8 ^c (±1)	15° (±2)	1	2–3	8 ^c (±1)	15 ^c (±2)	1	2–3		15 ° (±2)	1	1		
Induction treatment administration:cc venetoclax + atezolizumab + carboplatin + etoposide		X i	x	x			x	x			x٢	x						
Maintenance treatment administration: Venetoclax + atezolizumab															x	x		
Prophylactic cranial irradiation															Xs	хs		
Tumor response assessment	xt	X u									хu			1		xu		×۷
PK/ADA)	(w			X ^w				x w				See	x Appendix	3, Table 1	

Assessment or	Treatment Period ^a						Treatment Discon.	Survival Follow- Up									
Procedure	Period		I	ndu Cyc	ction le 1			Inde Cy (±3 I	uction /cle 2 Days) ^t)		rr (±:	nduction Cycles 3–4 3 Days) ^b	Maint. Cycle 1	Maint. Subseq. Cycles Every 21 Days (±3)	≤30 Days after Last Dose of Study Treatment	Every 3 Months After Disease Prog.
Day (Window)	–28 to –1	1	2 ^c	3	8 ^c (±1)	15 ^c (±2)	1	2–3	8 ^c (±1)	15 ^c (±2)	1	2–3	15 ° (±2)	1	1		
Blood Sample for biomarker analysis		x	x		x	x	x				x			x	C2D1, C3D1, C4D1 and every odd cycle	x See Appendix 4	
Tissue sample for biomarkers	x								s	Optio ee App	onal pendix	4				x See Appendix 4	
Optional tumor biopsy after induction treatment (if patient signs consent)														After tre	induction atment		
Optional tumor biopsy at the time of radiographic progression (if patient signs consent) ^x							At	the tin	ne of in	itial rac	liogra	ohic pro	gression				

Assessment or	Screening								Trea	itment	Perio	d ^a				Treatment Discon.	Survival Follow- Up
Procedure	Period		I	ndu Cyc	ction le 1			Inde Cy (±3 I	uction /cle 2 Days) ^b	,		ار (±:	nduction Cycles 3–4 3 Days) ^b	Maint. Cycle 1	Maint. Subseq. Cycles Every 21 Days (±3)	≤30 Days after Last Dose of Study Treatment	Every 3 Months After Disease Prog.
Day (Window)	–28 to –1	1	2 ^c	3	8 ^c (±1)	15 ^c (±2)	1	2–3	8 ^c (±1)	15 ^c (±2)	1	2–3	15 ° (±2)	1	1		
Optional tumor biopsy at other timepoints (RBR only)									Any tin	ne durir	ng stu	dy treat	ment or survival follo	ow-up	·		
Optional biopsy for DNA extraction (RBR only)												x					
Adverse events		x	х	x	x	x	x	х	ХУ	ХУ	x			x	x	X ^z	X ^z
Concomitant medications aa		x	x		x	x	x		x	x	x			x	x	x	
Survival and anti- cancer therapy follow-up																	x ^{bb}

ADA=anti-drug antibody; C=Cycle; CT=computed tomography; D=Day; discon. = discontinuation; ECOG=Eastern Cooperative Oncology Group; eCRF=electronic Case Report Form; FFPE=formalin-fixed paraffin-embedded; HBcAb=hepatitis B core antibody; HBsAg=hepatitis B surface antigen; HBV=hepatitis B virus; HCV=hepatitis C virus; maint. =maintenance; MRI=magnetic resonance imaging; PCI=prophylactic cranial irradiation; PCR=polymerase chain reaction; PD=pharmacodynamic; PD-L1=programmed death-ligand 1; PK=pharmacokinetic; PCI=prophylactic cranial irradiation; prog=progression; RBR=Roche Biosample Repository; RECIST=Response Evaluation Criteria in Solid Tumors; SCLC=small cell lung cancer; subseq. =subsequent; TLS=tumor lysis syndrome; TSH=thyroid-stimulating hormone. ^a Assessments should be performed before study drug infusion unless otherwise noted.

Atezolizumab—F. Hoffmann-La Roche Ltd Page 165 of 214 Protocol GO41864, Version 2

- ^b Cycle 1 must be performed within 5 days after the patient is enrolled. Screening assessments performed ≤ 96 hours before Cycle 1, Day 1 are not required to be repeated for Cycle 1, Day 1. In addition, ECOG performance status, limited physical examination, and local laboratory tests may be performed ≤ 96 hours before Day 1 of each cycle.
- Day 2, Day 8, and Day 15 assessments are not necessary during the dose-expansion phase, with the exception of PK sampling (refer to Appendix 4).
- ^d A pre-treatment tumor tissue (archival or freshly obtained) sample should be submitted before or within 4 weeks after enrollment. This specimen must be accompanied by the associated pathology report. Although any available tumor tissue sample can be submitted, it is strongly encouraged that representative tumor specimens in paraffin blocks (preferred) or 15 (or more) serial, freshly cut, unstained slides be submitted.
- Vital signs include pulse rate, respiratory rate, systolic and diastolic blood pressure, and temperature. Vital signs should be recorded as described in Section 4.5.4.
- ^f Includes evaluation of the head, eyes, ears, nose, and throat, and the cardiovascular, dermatologic, musculoskeletal, respiratory, gastrointestinal, genitourinary, and neurologic systems.
- ⁹ ECG recordings will be obtained when clinically indicated.
- ^h Hematology consists of CBC, including RBC count, hemoglobin, hematocrit, WBC count with differential (neutrophils, lymphocytes, eosinophils, monocytes, basophils, and other cells), and platelet count.
- At screening, the patient must have adequate hematologic and end-organ function defined by laboratory test results obtained within 14 days prior to enrollment.
- ^j Serum chemistry includes BUN or urea, sodium, potassium, magnesium, chloride, bicarbonate or total CO² if considered standard of care in the region, glucose, total bilirubin, ALT, AST, alkaline phosphatase, LDH, total protein, and albumin.
- ^k TLS assessment frequency during the dose-expansion phase will be determined based on a comprehensive review of data in the dose-escalation phase. TLS labs include serum creatinine, calcium, phosphorous, uric acid, potassium, and LDH. If the screening assessments were done within 3 days prior to Cycle 1 Day 1, there is no need to repeat the TLS panel at Cycle 1 Day 1. Refer to Appendix 9 and Appendix 11 for further instructions.
- ¹ Serum pregnancy test within 14 days before Cycle 1, Day 1.
- ^m Urine pregnancy tests; if a urine pregnancy test result is positive, it must be confirmed by a serum pregnancy test.
- ⁿ Total T3 will be tested only at sites where free T3 is not performed.
- Thyroid function testing (TSH, free T3, free T4) collected on Day 1 of Cycles 1, 4, 8, and 12, and every fourth cycle thereafter.
- P All patients will be tested for HIV prior to the inclusion into the study and HIV-positive patients will be excluded from the study. Patients with active hepatitis B (chronic or acute; defined as having a positive HBsAg test result at screening) will be excluded from the study. Patients with past or resolved HBV infection (defined as the presence of HBcAb and absence of HBsAg) are eligible; HBV DNA should be obtained in these patients prior to enrollment. Patients with HCV will be excluded from the study; patients who test positive for HCV antibody are eligible only if PCR is negative for HCV RNA.
- ^q Urinalysis by dipstick (specific gravity, pH, glucose, protein, ketones, and blood). Urinalysis is required at screening and will be obtained when clinically indicated.
- ^r For atezolizumab, the initial dose will be administered over 60 (± 15) minutes. If the first infusion is well tolerated, subsequent infusions may be administered over 30 (± 10) minutes. For carboplatin and etoposide, study drug will be administered as described.

Atezolizumab—F. Hoffmann-La Roche Ltd

Page 166 of 214 Protocol GO41864, Version 2

- ^t CT scans (with oral/IV contrast unless contraindicated) or MRI scans of the chest and abdomen. A CT or MRI scan of the pelvis is required at screening and as clinically indicated or as per local standard of care at subsequent response evaluations. A CT (with contrast) or MRI scan of the head must be done at screening to evaluate CNS metastasis in all patients.
- ^u Perform every 6 weeks (± 7 days) for 48 weeks following Cycle 1, Day 1 and then every 9 weeks (± 7 days) thereafter, after completion of the Week 48 tumor assessment, regardless of treatment delays, until radiographic disease progression per RECIST v1.1, withdrawal of consent, death, or study termination by the Sponsor, whichever occurs first. Patients who continue treatment beyond radiographic disease progression per RECIST v1.1, will undergo tumor assessments at the frequency described above until study treatment is discontinued.
- If the patient discontinued study treatment for any reason other than radiographic disease progression per RECIST v1.1 (e.g., toxicity, symptomatic deterioration), tumor assessments will continue at the same frequency as would have been followed if the patient had remained on study treatment (i.e., every 6 weeks [± 7 days] for 48 weeks following Cycle 1, Day 1 and then every 9 weeks [± 7 days] thereafter) until radiographic disease progression per RECIST v1.1, withdrawal of consent, death, or study termination by the Sponsor, whichever occurs first, even if the patient starts another anti-cancer therapy after study treatment discontinuation, unless consent is withdrawn.

w See Appendix 3, Table 2.

- Optional tumor biopsy at radiographic disease progression, if clinically feasible, preferably within 40 days of radiographic progression or prior to start of the next anti-cancer therapy, whichever occurs is sooner.
- Phone call from the site to the patient to assess adverse events as described in Section 5.2.1. The rationale for this phone call is to characterize the impact of and response to treatment, such assessments allow follow-up that is more frequent than the visit, which is every 3 weeks, will be useful in management.
- ² All serious adverse events and adverse events of special interest, regardless of relationship to study drug, will be reported until 90 days after the last dose of study drug or initiation of new systemic anti-cancer therapy after the last dose of study drug, whichever occurs first. All other adverse events, regardless of relationship to study drug, will be reported until 30 days after the last dose of study drug or initiation of new systemic anti-cancer therapy after the last dose of study drug or initiation of new systemic anti-cancer therapy after the last dose of study drug or initiation of new systemic anti-cancer therapy after the last dose of study drug or initiation of new systemic anti-cancer therapy after the last dose of study drug, whichever occurs first. After this period, all deaths should continue to be reported. In addition, the Sponsor should be notified if the investigator becomes aware of any serious adverse event or adverse event of special interest that is believed to be related to prior exposure to study treatment. These events should be reported through use of the Adverse Event eCRF.
- ^{aa} From 7 days before screening until the treatment discontinuation visit. All such medications should be reported to the investigator and recorded on the Concomitant Medications eCRF.
- ^{bb} Survival follow-up information will be collected via telephone calls, patient medical records, and/or clinic visits every 3 months or more frequently until death, loss to follow-up, or study termination by the Sponsor, whichever occurs first. All patients will be periodically contacted for survival and new anti-cancer therapy information unless the patient requests to be withdrawn from follow-up (this request must be documented in the source documents and signed by the investigator). If the patient withdraws from the study, study staff may use a public information source (e.g., county records), when permissible, to obtain information about survival status only.
- ^{cc} On Day 1 of each cycle, patients will receive treatment in the following order: 1) atezolizumab, 2) carboplatin, 3) etoposide, and 4) venetoclax. On Days 2 and 3, patients will receive etoposide infusions. Refer to Section 4.3.2 for specific details. Venetoclax is administered QD for 7 or 14 days as described in Section 3.1.2.

Atezolizumab—F. Hoffmann-La Roche Ltd

Page 167 of 214 Protocol GO41864, Version 2

^s During the maintenance phase, PCI is permitted as per local standard of care and will be reported on the Prophylactic Cranial Irradiation eCRF.

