Patients initially treated in the induction arm who tolerate study treatment without excessive toxicity, and have not undergone disease progression, will then proceed to maintenance treatment with venetoclax plus atezolizumab. The venetoclax dose for the maintenance setting in Arm B will be the dose that has been cleared in the maintenance-only arm (Arm A) of the study (maintenance RP2D, RP2D-M). The venetoclax RP2D for the induction setting (induction RP2D, RP2D-I) will be based on the MTD of venetoclax in combination with atezolizumab, carboplatin and etoposide.

During the maintenance phase in either Arm A or Arm B, prophylactic cranial irradiation (PCI) is permitted (though not mandated) prior to the commencement of maintenance therapy per local standard of care. Due to the lack of data with concurrent use of PCI with either atezolizumab or venetoclax, concurrent administration of PCI during maintenance therapy is not permitted. PCI will be reported on the Prophylactic Cranial Irradiation electronic Case Report Form (eCRF). Consolidative thoracic radiation with curative intent or the intent to eliminate residual disease is not permitted. Palliative radiation for symptomatic management is allowed (refer to Section 4.4.1 for further details).

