3.1.3 Definition of Dose-Limiting Toxicity

Patients will be closely monitored for adverse events during a DLT assessment period, which starts on Day 1 of Cycle 1 and continues through Day 1 of Cycle 2. *The DLT assessment period is the same for maintenance phase (Arm A) and induction phase (Arm B).* Adverse events meeting criteria for DLT within the assessment period must be

Venetoclax—F. Hoffmann-La Roche Ltd Page 56 of 214 Protocol GO41864, Version 1 reported to the Sponsor within 24 hours. The expected start of Cycle 2 would be on Day 22 if there are no treatment delays. The same DLT criteria will be used in the maintenance and induction settings.

Determination of whether a patient is evaluable for DLT assessment will be made in accordance with the following rules:

- Patients who receive study treatment and remain on study through the DLT assessment period will be considered DLT-evaluable.
- Patients who discontinue from treatment with venetoclax prior to completing the DLT assessment period for reasons other than a DLT will be considered non-evaluable for dose-escalation decisions and MTD determination, and will be replaced by an additional patient at that same dose level.
- Patients who receive less than 50% of planned venetoclax doses during the DLT assessment period will be considered non-evaluable for dose-escalation decisions and will be replaced by another patient in that cohort.

A DLT is defined in this trial as any one of the following events occurring during the DLT assessment period and is assessed by the investigator as possibly being related to study treatment.

The following events will be considered DLTs only if they are associated with treatment delay beyond 14 days in initiating Cycle 2, Day 1:

- Grade 4 thrombocytopenia (platelet count <25,000/mm³)
- Grade 3 thrombocytopenia with severe bleeding
- Grade 4 anemia
- Grade 4 neutropenia (absolute neutrophil count [ANC] < 500/µL)

The following events will be considered DLTs regardless of whether they result in a treatment delay:

- Any treatment-related death
- Grade 3 febrile neutropenia lasting for more than 7 days with growth factor support and supportive care
- Grade 4 febrile neutropenia of any duration
- Grade ≥ 3 diarrhea, nausea, or vomiting lasting for ≥ 72 hours despite adequate treatment and supportive care (e.g., anti-emetics, anti-diarrheals, etc.)

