- Laboratory TLS lasting for ≥ 7 days with best supportive care or clinical TLS according to the Howard criteria (Howard et al. 2011)
- Treatment related Grade ≥ 3 non-hematologic, non-hepatic toxicities lasting for ≥72 hours

- Laboratory abnormalities consistent with Hy's Law will be considered a DLT. Hy's Law is defined as AST and/or ALT elevation > 3 × ULN, in conjunction with an elevation in total bilirubin to > 2 × ULN, without findings of cholestasis (ALP within normal limits), in patients for whom no other cause of hepatotoxicity is evident.
- All study treatment-related adverse events requiring permanent discontinuation of any of the study drugs

3.1.4 Dose-Escalation Rules, Determination of Dose-Limiting Toxicities, and Recommended Phase II Dose

Dose-escalation for venetoclax in the maintenance only (Arm A) as well as in the induction and maintenance (Arm B) settings will occur in accordance with the rules listed below.

Arm A (Refer to Figure 3):

- A minimum of 3 DLT-evaluable patients will initially be enrolled into each cohort.
- If none of the first 3 DLT-evaluable patients experiences a DLT, enrollment of the next cohort at the next dose level may proceed.
- If 1 of the first 3 DLT-evaluable patients experiences a DLT, the cohort will be expanded to 6 patients. If there are no further DLTs in the first 6 DLT-evaluable patients, enrollment of the next cohort at the next dose level may proceed.
- If 2 or more of the first 6 DLT-evaluable patients in the cohort experience a DLT, an additional 3 patients will be evaluated for DLTs at a lower dose level. If none of the first 3 DLT-evaluable patients experiences a DLT, the MTD in maintenance will have been reached.
- If 1 of the first 3 DLT-evaluable patients *at a lower* dose level experiences a DLT, *this* cohort will be expanded to 6 patients. If there are no further DLTs in the first 6 DLT-evaluable patients, the MTD in maintenance will have been reached.
- If 2 or more of the first 6 DLT-evaluable patients in the *lower* dose *level* cohort experience a DLT, the MTD will have been exceeded and dose-escalation in maintenance will stop.
- If the MTD is exceeded at any dose level, the highest dose at which fewer than 2 of 6 DLT-evaluable patients (i.e., ≥ 33%) experience a DLT will be declared the MTD.

If the MTD is not exceeded at any dose level, the highest dose of venetoclax (800 mg) administered in maintenance will be declared the MTD for the maintenance setting.

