6. STATISTICAL CONSIDERATIONS AND ANALYSIS PLAN

6.1 DETERMINATION OF SAMPLE SIZE

The estimated sample size of the dose-escalation phase follows from the doseescalation rules of a standard 3+3 algorithm. It is anticipated that enrollment of two cohorts of 3–6 patients each in the maintenance phase, as well as up to five cohorts of 3–6 patients each in the induction phase, for a total of 18–42 patients, will be required to establish the RP2D for maintenance (RP2D-M) and the RP2D for the induction setting (RP2D-I) during the dose-escalation phase.

A sample of 20 patients will be sufficient to provide adequate precision for the point estimates. Assuming an observed ORR of 80% for the induction plus maintenance setting (Arm B), with 20 patients, the lower bound of the two-sided 80% CI will rule out a probability of response of 63%. Assuming an observed ORR of 5% for the maintenance-only setting (Arm A), with 20 patients, the lower bound of the two-sided 80% CI will rule out a probability of response of 0%.

An 80% CI for true underlying ORR values of 0.05, 0.1, 0.7, 0.75, and 0.8 are provided in Table 13.

Table 13Operating Characteristics for Proposed Study Design for Several
Possible True Underlying Overall Response Rate

		Tru	e Underlying	ORR	
	5%	10%	70%	75%	80%
80% confidence interval for true ORR	(1%, 18%)	(3%, 24%)	(53%, 83%)	(59%, 87%)	(64%, 91%)

^a Confidence intervals are based on the assumption that the point estimate is equal to the true underlying value of the objective response rate (ORR) in each column.

For a given adverse event with a true rate of 10%, 5%, or 1%, the probability of observing at least one such event in a cohort of 20 patients is 87.8%, 64.2%, and 18.2%, respectively. Table 14 describes exact 90% CIs for a range of observed proportions of adverse events based on a sample size of 20 patients.

Exact 90% Confidence Interval for the Potential Adverse Event Rates
(0%, 16%)
(0%, 22%)
(2%, 28%)
(7%, 40%)
(14%, 51%)
-

Table 14 90% Confidence Interval Estimates for Potential Adverse Event Rates

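### Appendices 1 and 2 permit PCI during the maintenance cycles, which Section 3.1.2.2 and the synopsis prohibit

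*Combined protocol and SAP*

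**What the plan says.** Section 3.1.2.2 covers patients in either arm. It makes PCI optional and places it "prior to the commencement of maintenance therapy per local standard of care". It then says that "concurrent administration of PCI during maintenance therapy is not permitted" and gives the reason: data on combining PCI with either study drug are lacking. The synopsis repeats this rule.

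The schedules of activities carry a different message. Appendix 1 (maintenance only) and Appendix 2 (induction plus maintenance) each have a row headed "Prophylactic cranial irradiation", marked at Maintenance Cycle 1 and at the subsequent maintenance cycles. Footnote s, attached to those marks in both appendices, reads: "During the maintenance phase, PCI is permitted as per local standard of care and will be reported on the Prophylactic Cranial Irradiation eCRF".

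Section 3.1.3 defines the DLT window as the period "which starts on Day 1 of Cycle 1 and continues through Day 1 of Cycle 2".

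**The concern.** The footnote keeps the permission and the reporting instruction but drops both the timing limit and the ban. The rows then mark the period in which PCI is barred and leave unmarked the period in which it is allowed. Section 4.5 sends sites to these two appendices and expects every listed activity to be carried out and documented, so the schedule is an operative instruction.

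Two things are at stake. The first is patient safety: a site could give cranial irradiation together with venetoclax and atezolizumab, an exposure the sponsor has ruled out for lack of data. The second is dose finding in Arm A. Under Section 3.1.3 an event counts as a DLT only if the investigator judges it possibly related to study treatment. Table 12 in Section 5.3.4 asks, among other things, whether concomitant therapy readily explains the event. PCI inside the window could lead a true DLT to be discounted, or an effect of irradiation to be counted as a DLT.

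**Working it through.** **Step 1: set the texts side by side.**

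| Place | PCI before maintenance therapy | PCI during maintenance therapy |
|---|---|---|
| Section 3.1.2.2 and synopsis | Permitted, optional | Not permitted |
| Appendices 1 and 2, PCI row | No mark | Marked at Cycle 1 and at subsequent cycles |
| Appendices 1 and 2, footnote s | Not mentioned | Permitted, no limit stated |
| Section 3.1.2.1 (Arm A) | Silent | Silent |
| Sections 4.4.1 and 4.4.2 | PCI not named | PCI not named |

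The PCI marks stand in the same columns as the row for administering venetoclax plus atezolizumab.

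**Step 2: can the marks mean PCI given before therapy?** At Cycle 1, Day 1 this is arguable, because the schedules ask for assessments before infusion. At subsequent cycles it is not. Section 3.1.2.1 gives maintenance venetoclax on Days 1–21 of a 21-day cycle, and Section 4.3.1.2 says continuous dosing runs with no break between cycles. The planned drug-free time per cycle is 21 − 21 = 0 days, so unless dosing is interrupted, PCI at any later maintenance cycle is concurrent.

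**Step 3: who has Maintenance Cycle 1 as the DLT window?** Section 6.1 plans "enrollment of two cohorts of 3–6 patients each in the maintenance phase", which gives 2 × 3 = 6 to 2 × 6 = 12 Arm A escalation patients. This is the number to whom the window applies, not the number expected to receive PCI. Twelve is not a strict ceiling: Section 3.1.2.1 allows a possible 200 mg cohort, and Section 3.1.3 replaces non-evaluable patients. In Arm B the DLT window is induction Cycle 1, so PCI in maintenance would not affect that arm's DLT count.

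**Step 4: how sensitive is the Arm A decision to one event?** Section 3.1.4 states: "If 1 of the first 3 DLT-evaluable patients experiences a DLT, the cohort will be expanded to 6 patients". Its rules give:

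- 0 of 3 (0%): escalate. 1 of 3 (33%): expand to 6.
- 1 of 6 (17%): escalate. 2 of 6 (33%): go to a lower dose.

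At either boundary one wrongly attributed event changes the action. The maintenance dose recommended from Arm A is then used in the maintenance part of Arm B (Section 3.1.2).

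**The case against.** The strongest reply is that the protocol already forbids the combination clearly. The ban is stated twice, with a reason, and names both arms even though it sits under the Arm B heading. Section 4.4.2 prohibits radiotherapy intended to treat cancer during study treatment, apart from palliative radiotherapy and certain local therapy, and Section 4.4.1 does not list PCI as permitted. Footnotes next to the treatment rows refer sites to Section 3.1.2, which contains the ban. Section 3.1.2.2 itself uses the term maintenance phase for the period just before the first dose, so footnote s could be an abbreviation and the marks mere reporting prompts.

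Part of this stands. The intended design is clear, so this is an inconsistency between schedule and text and not a flaw in the design. Section 4.4.2 also leans towards the ban. But that section speaks of treating cancer and names neither PCI nor prophylaxis, so it does not plainly override a specific footnote saying PCI is permitted. Neither the pre-dose reading nor the reporting reading accounts for the mark at subsequent cycles together with an unqualified permission.

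It is also fair to say that the harm depends on a site following the schedule over the body text. PCI is optional, the Arm A eligibility criteria allow up to 56 days between the last chemotherapy dose and maintenance, and the documents say nothing about which listed DLT events PCI might produce.

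**Conclusion.** The concern holds. Both schedules permit, in the columns where maintenance drugs are dosed, a procedure that Section 3.1.2.2 and the synopsis bar in that period. This is current operative text and should be corrected.

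The number of patients who would receive concurrent PCI cannot be estimated: no rate is given, and it may be low. What can be stated is that 6 to 12 planned Arm A escalation patients have their DLT window in a marked column, and that one event is enough to change a cohort decision. The safety argument applies more widely, because the two appendices cover maintenance in both escalation and expansion.

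The conclusion assumes that some sites will work from the schedule of activities. That is an inference, but a reasonable one given Section 4.5.

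**What to change.** Let the reasoned prohibition in Section 3.1.2.2 and the synopsis govern, and change the schedules to match it.

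- In Appendices 1 and 2, remove the PCI marks from the Maintenance Cycle 1 and subsequent-cycle columns, or move them to a column that precedes the first maintenance dose.
- In both appendices, replace footnote s with: *PCI is permitted only before the first dose of maintenance therapy, per local standard of care, and not concurrently with maintenance therapy (see Section 3.1.2.2); report on the PCI eCRF.*

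The cost is two table rows and two footnotes. Nothing changes in the design, the sample size or the data collected.
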